## 11.2 Ethical Conduct of the Clinical Study

This clinical study will be conducted in accordance with the protocol, the HELSINKI declaration (1964) and its subsequent amendments, ICH GCP, national regulations, and in compliance with other applicable regulatory requirements.

## 11.3 Subject Information and Consent

All subjects who participate in this clinical study are required to be fully informed about the clinical study in accordance with GCP guidelines, national regulations and guidelines, and in accordance with local requirements.

The ICF, approved by an IEC, will be fully explained to the subject. The subject must agree to photo consent in order to participate in the clinical study.

Prior to enrollment into the clinical study, the subject and the PI or designee must sign and date the consent form(s). The Investigator is responsible for maintaining each subject's consent form(s) in the Investigator's Site File and providing each subject with a copy of the signed and dated consent form(s).

## 11.4 Protection of Personal Data

For the purposes of the study, the Sponsor is considered the data controller, and the Institution and PI are both considered to be data processors.

All processing of personal data must be carried out in accordance with national legislation concerning the protection of personal data. The Institution and PI are responsible for complying with all requirements pursuant to national legislation in the country in which the Institution and PI are located. The Sponsor will ensure that all requirements are complied with for data processing, which is carried out in Sweden by the Sponsor. Institution and PI are aware of, and will obtain the required approvals prior to the transfer of sensitive personal data which is subject to pre-approval, prior to the transfer of such data outside Europe.

The ICF shall contain information about which personal data will be collected in the study and that the data will be kept confidential. The provided information shall be sufficient to enable all subjects to give their consent not only to the participation in the study, but also to the processing of personal data. Such information includes information regarding the purposes of data collection processing, data transfer to countries outside of Europe, and the length of time during which the personal data will be stored. The subject shall have the right to access the stored personal data, and the right to correct any incorrect or obsolete information. If a subject decides to terminate the study prematurely, data collected before withdrawn consent will be used in the evaluation of the study, however no new data may be collected. Authorized representatives from the Sponsor or a RA may visit the study site to perform audits/inspections, including source data verification, i.e., comparing data in the subjects' medical records and the eCRF. Data and information shall be handled strictly confidential.

	Title 05PF2005 Clinical Study Protocol - STAR	Doc id MA-48441
--	--	----------------------------------

## 11.5 Contractual Requirements

The clinical trial agreement (CTA) outlines the compensation and payment terms of the study. The CTA must be signed before the first subject is screened in the study. If there are differences between the CTA and the CSP regarding certain rights and obligations, the CTA is the prevailing document.

## 11.6 Data Collection and Archiving

### 11.6.1 Data Collection

The Investigator must maintain all required records for all subjects. The data for this clinical study will be recorded in the subject's source documents and in the eCRFs. All data should be recorded in the eCRFs completely and promptly.

### 11.6.2 Source Documentation

The eCRF is considered a data entry form and does not constitute the original (or source) medical records unless otherwise specified. Source documents are all documents used by the Investigator or hospital that relate to the subject's medical history, verifying the existence of the subject, the inclusion and exclusion criteria, and all records covering the subject's participation in the study.

The source data location log specifies what data that shall be available in the medical record. The source data location log shall also specify the data for which the eCRF serves as the source. Such data only need to be recorded in the eCRF and are typically associated with study-specific procedures and not with normal clinical care practice. For this type of study data the Investigator would not be expected to duplicate the information into the medical record.

The PI is responsible for maintaining adequate source documentation. Source data should be attributable, legible, contemporaneous, original, accurate, and complete. Changes to source data should be traceable, i.e., without obscuring the original data entry and with an explanation if necessary.

Source documents shall be made available for inspection by the monitor at each monitoring visit, as well as during audits and/or inspections.

### 11.6.3 Archives

All pertinent data, samples, photographs, correspondence, and reports, the original or amended CSP, and all other material relating to the clinical study will be maintained securely in the Sponsor/CRO/Investigator/Institution archives for the legally required duration for archiving.

The Investigator/Institution should maintain the essential clinical study documents according to the applicable regulatory requirements.

 EST. 1981	Title 05PF2005 Clinical Study Protocol - STAR	Doc id MA-48441
---	--	----------------------------------

Effective date: 2021-12-01 17:39

Effective

Version: 5.0

The Investigator/Institution should take measures to prevent accidental or premature destruction of these documents.

If the PI retires, relocates, or withdraws from the responsibility of keeping the clinical study records for any reason, custody must be transferred to a person who will accept the responsibility. The Sponsor/CRO must be notified in writing of the name and address of the new custodian.

### 11.7 Insurance

Q-Med AB's obligations in this clinical study are covered by Galderma's global general liability program. An insurance certificate will be provided upon request. The institution/PI is obligated to maintain insurance coverage for their obligations in the clinical study according to the CTA.

### 11.8 Publication Policy

The obligation of the Institution/PI and Sponsor regarding intellectual property rights, confidentiality, and publications are described in detail in the CTA.

The aim is to submit the results of this study for publication in the public database (<http://www.clinicaltrials.gov>) and to a peer-reviewed medical journal for publication. Each person listed as an author of the results of this multicenter study shall have made a substantial, direct, and intellectual contribution to the work. Authorship will be based on: (1) substantial contributions to the conception or design of the work; or the acquisition, analysis, or interpretation of data for the work; (2) drafting the work or revising it critically for important intellectual content; (3) final approval of the version to be published; and (4) agreement to be accountable for all aspects of the work in ensuring that questions related to the accuracy or integrity of any part of the work are appropriately investigated and resolved.a Conditions 1, 2, 3, and 4 must all be met in order to be designated as an author. Those who do not meet all four criteria will be acknowledged. Among the authors that fulfill the above-mentioned criteria, one author will be appointed by the Sponsor to take primary responsibility for the overall work as primary author.

---

a Defining the role of authors and contributors, compiled by the International Committee of Medical Journal Editors (ICMJE) (<http://www.icmje.org>).

GALDERMA EST. 1981	Title 05PF2005 Clinical Study Protocol - STAR	Doc id MA-48441
-----------------------	---	---------------------------

### 13. SUMMARY OF CHANGES

Section in the clinical study protocol	Rational for changes	Description of changes
Synopsis	As per request from EC no interim analysis will be performed.	Removed possibility to perform an interim analysis before study completion.
7.2.1.2.2 Procedure for Reporting a Serious Adverse Event (SAE)	Updated to match the SAE reporting process.	Added “Print and complete the SAE form” under bullet 3.
9.2.1 Interim Analysis	As per request from EC no interim analysis will be performed.	Removed possibility to perform an interim analysis before study completion.
Appendix 4, 5 and 6	Request from EC to remove signature row for subject questionnaires to protect pseudo-anonymisation.	Removed signature row.

**Note:** Minor corrections and editorial changes are not listed above.

GALDERMA EST. 1981	Title 05PF2005 Clinical Study Protocol - STAR	Doc id MA-48441
-----------------------	---	---------------------------

## 14. APPENDICES

### Appendix 1 Preparation of Alluzience and Reconstitution of powder BoNT-A

#### Alluzience Preparation Questionnaire

Time for study product to equilibrate to room temperature

*(Note: should be 15 – 30 min according to CSP)*

     
MM:SS

How long did it take to prepare the product to have it ready for injection?

*Time from opening the outer box to having a syringe ready for use.*

     
MM:SS

Did you prepare the product in front of the subject?

Yes  No

I did not experience any technical issues/problems when using a ready to use product as compared to a product to be reconstituted

Strongly agree

Agree

Neither agree nor disagree

Disagree

Strongly disagree

	Title 05PF2005 Clinical Study Protocol - STAR	Doc id MA-48441
--	--	----------------------------------

## BOTOX/Vistabel Reconstitution Questionnaire

**NOTE: Reconstitution information can be found on the next page.**

Time for solvent to equilibrate to room temperature  
*(Note: should be 15 – 30 min according to CSP)*

--	--	--	--

MM:SS

How long did it take to prepare the product to  
 have it ready for injection?

--	--	--	--

MM:SS

*Time from opening the outer box to having a syringe  
 ready for use.*

Did you reconstitute in front of the subject?

Yes  No

Any product problems associated with the reconstitution?

Yes  No

If "Yes" above:

- Wrong final concentration (U/mL)
- Wrong concentration of NaCl used/wrong diluent used
- Vacuum not pulling the solvent into the vial
- Difficulties to insert the needle into the vial
- Particles in solution
- Bubble/Foam formation
- Waste of product

Other, please describe: \_\_\_\_\_  
 \_\_\_\_\_  
 \_\_\_\_\_  
 \_\_\_\_\_

Have you ever had any issues to reconstitute the powder BoNT-A in the past? Yes  No

If "Yes" above:

- Wrong final concentration (U/mL)
- Wrong concentration of NaCl used/wrong diluent used
- Vacuum not pulling the solvent into the vial
- Difficulties to insert the needle into the vial
- Particles in solution
- Bubble/Foam formation
- Waste of product

Other, please describe: \_\_\_\_\_  
 \_\_\_\_\_  
 \_\_\_\_\_

	Title 05PF2005 Clinical Study Protocol - STAR	Doc id MA-48441
--	--	----------------------------------

Remember to follow the reconstitution description in the summary of product characteristics (see list below), any deviation (e.g. removing the rubber cap should be recorded as a protocol deviation).

- Reconstitution should be performed in accordance with good practices rules, particularly for the respect of asepsis.
- BOTOX®/VISTABEL® has to be reconstituted with sterile unpreserved normal saline solution (0.9% sodium chloride solution for injection). As per the dilution table below, the requested amount of sterile unpreserved normal saline solution (0.9% sodium chloride solution for injection) has to be drawn up into a syringe in order to obtain a reconstituted solution at a concentration of 4 Units/0.1 mL

Vial size	Amount of solvent added (sterile unpreserved normal saline solution (0.9% sodium chloride solution for injection))	Resulting dose (Units per 0.1 mL)
50 Units	1.25 mL	4.0 Units

- To avoid BOTOX®/VISTABEL® denaturation, the solution is prepared by injecting the solvent slowly into the vial and by gently rotating the vial avoiding bubble formation.
- The vial has to be discarded if the vacuum does not pull the solvent into the vial.

Once reconstituted, the solution should be visually inspected prior to use. Only clear, colourless to slightly yellow solution without particles should be used.

2021-12-01 17:39

Effective date:

Effective

Version: 5.0

## Appendix 2 Investigator Treatment Session Questionnaire (for Alluzience only)

NOTE: To be answered for Alluzience only	Strongly agree	Agree	Neither agree nor disagree	Disagree	Strongly disagree
1. I prefer to utilize a ready to use product as compared to a product to be reconstituted					
2. I could dedicate more time to explain the treatment procedure in using a ready to use product as compared to a product to be reconstituted					
3. I could save time on the reconstitution and injection procedure to do something else					
4. I felt more relaxed/less stressed in not having to reconstitute the product to be injected					
5. I feel more secure when I have a pre-diluted solution and don't have to reconstitute the product myself					
6. I have a good feeling about injecting a modern and innovative product as compared to the reconstituted product					
7. I feel I am more precise in my injection with a ready to use product compared to a product to be reconstituted					
8. I like to propose new innovative treatment with liquid ready to use product to my patient					
9. I produced substantially less waste of non-toxin material (syringes, needles, saline etc.) using ready-to-use product as compared to the reconstituted product					
10. When I use a ready to use toxin I spend less materials for injection					
11. I believe that the use of ready to use toxin is better for the environment as I produce less waste					
12. I feel more confident when injecting a product free from animal and human excipients					

CONFIDENTIAL

Page 64 of 71

GALDERMA EST. 1981	Title 05PF2005 Clinical Study Protocol - STAR	Doc id MA-48441
------------------------------	--	----------------------------------

Effective date: 2021-12-01 17:39

*Effective*

Version: 5.0

CCI

Effective date: 2021-12-01 17:39

*Effective*

Version: 5.0

CCI

GALDERMA EST. 1981	Title 05PF2005 Clinical Study Protocol - STAR	Doc id MA-48441
------------------------------	--	----------------------------------

Effective date: 2021-12-01 17:39

*Effective*

Version: 5.0

CCI

*Effective*

Effective date: 2021-12-01 17:39

CCI

Version: 5.0

[figure not shown]
GALDERMA EST. 1981	Title 05PF2005 Clinical Study Protocol - STAR	Doc id MA-48441
------------------------------	--	----------------------------------

*Effective*

Version: 5.0

Effective date: 2021-12-01 17:39

CCI

Effective date: 2021-12-01 17:39

*Effective*

Version: 5.0

CCI

GALDERMA <small>EST. 1981</small>	Title 05PF2005 Clinical Study Protocol - STAR	Doc id MA-48441
--------------------------------------	---	---------------------------

1.0 PURPOSE

This statistical analysis plan (SAP) describes the methods to be used in the analysis of study data from Galderma STAR Protocol in order to answer the study objectives, and is based on version 5.0 of the study protocol, dated December 1, 2021, and version 1.0 of the electronic case report forms (eCRF), dated January 27, 2022.

Populations for analysis, data handling rules, statistical methods, and formats for data presentation are described within this document. The statistical analyses and summary tabulations described in this SAP will provide the basis for the results sections of the clinical study report (CSR) for this study. The SAP outlines any differences in data analysis methods relative to those planned in the study protocol.

2.0 ABBREVIATIONS

Below is the list of abbreviations that will be used throughout this document.

Abbreviation	Definition
AC	Advanced Clinical
AE	Adverse Event
ATC	Anatomical Therapeutic Chemical
BMI	Body Mass Index
BoNT-A	Botulinum Neurotoxin Type A
CDISC	Clinical Data Interchange Standards Consortium
CSP	Clinical Study Protocol
CSR	Clinical Study Report
eCRF	Electronic Case Report Form
eCTD	Electronic Common Technical Document
FAS	Full Analysis Set
GAIS	Global Aesthetic Improvement Scale
GL	Glabellar Lines
ICH	International Council for Harmonization
Max	Maximum
MedDRA	Medical Dictionary for Regulatory Activities
Min	Minimum
N	Number of Observations

Abbreviation	Definition
OC	Observed Case
PD	Protocol Deviation
PP	Per-Protocol
PT	Preferred Term
SAE	Serious Adverse Event
SAP	Statistical Analysis Plan
SD	Standard Deviation
SOC	System Organ Class
TEAE	Treatment-Emergent Adverse Event
WHO	World Health Organization

3.0 OVERALL STUDY DESIGN AND OBJECTIVE

3.1 Study Objectives

3.1.1 Primary Study Objective

The primary objective of this study is to evaluate the time needed to prepare Alluzience and powder Botulinum Neurotoxin Type A (BoNT-A) according to protocol.

3.1.2 Secondary Study Objectives

The secondary objectives of the study are:

1. To evaluate preparation/reconstitution experience of Alluzience and powder BoNT-A.
2. To describe Investigator treatment experience when using Alluzience for the treatment of Glabellar Lines (GL).

CCI

CCI

CCI

3.1.4 Safety Study Objective

The safety objective is to evaluate the safety of a single dose of Alluzience for the treatment of moderate to severe GL.

3.2 Study Design

This is an open-label, randomized, interventional, two-armed, multi-centre study to investigate subject treatment perception and Investigator treatment experience when using Alluzience or vacuum-dried BoNT-A (powder BoNT-A) for treatment of GL. Subjects randomized to be treated with powder BoNT-A will only be followed for 1 month (Visit 3) while subjects treated with Alluzience will be followed for 6 months (Visit 6).

3.3 Treatments and Assignment to Treatments

As a screen failure rate of approximately 10% is anticipated, approximately 170 subjects will be screened. Approximately 150 subjects will be randomized to either Alluzience or powder BoNT-A treatment in a CCI ratio. Randomization will be stratified by study site.

3.4 Determination of Sample Size

The sample size of approximately 150 subjects, 100 subjects in the Alluzience treatment group and 50 in the powder BoNT-A treatment group, is not based on a statistical calculation. The selected number of subjects is regarded as sufficient for an evaluation of the studied endpoints by using descriptive statistics.

4.0 GENERAL ANALYSIS CONVENTION

CCI

CCI

4.1 Trial Periods

4.1.1 Alluzience Group

The study consists of six visits for the Alluzience group: screening (Visit 1), treatment (Baseline/Visit 2) and four follow-up visits at 1 (Visit 3), 3 (Visit 4), 5 (Visit 5) and 6 (Visit 6) months after treatment. The screening visit and the treatment visit might be conducted at the same day.

4.1.2 Powder BoNT-A Group

The study consists of three visits for the powder BoNT-A group: screening (Visit 1), treatment (Baseline/Visit 2) and a follow-up visit at Month 1 (Visit 3). The screening visit and the treatment visit might be conducted at the same day.

4.2 Visit Windows

Study visits are expected to occur according to the protocol schedule (Appendix A). When necessary, unscheduled visits may be conducted, in particular if an AE occurs and needs to be assessed and/or treated. Questionnaire scores for unscheduled visits will only be included in data listings. All data will be tabulated per the evaluation visit as recorded on the eCRF. In data listings, the relative study day of all dates will be presented.

If date of assessment \geq date of first dose of study drug:

Relative Study Day = [date of assessment – date of first dose of study drug] + 1

If date of assessment $<$ date of first dose of study drug:

Relative Study Day = date of assessment – date of first dose of study drug

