## SCHEDULE OF ASSESSMENTS

**Table 2 Schedule of Assessments**

1 month = 4 weeks/28 days Visit windows are calculated from Baseline/Visit 2 if not otherwise specified.	Visit 1 Group 1 and 2	Visit 2 Group 1 and 2	Visit 3/ Group 1 EoS Group 2	Visit 4 Group 1	Visit 5 Group 1	Visit 6/ET EoS Group 1
	Screening 	Treatment/ Baseline  (within 3 weeks after screening)	1-Month Follow-up (±7 days)	3-Month Follow-up (±7 days)	5-Month Follow-up (±7 days)	6-Month Follow-up (±7 days)
Informed Consent	X	(X) 				
Demographic Data including, medical history & con-current diseases, previous facial treatments/ procedures	X	(X) 				
Inclusion /Exclusion Criteria	X	X				
Adverse Events 		X	X	X	X	X
Concomitant Medication/ Procedures	X	X	X	X	X	X
Urine Pregnancy Test 	X	X				
Photography		X	X	X		X
Randomization		X				
Treatment		X				
End of study 			X Group 2, powder BoNT-A			X Group 1, Alluzience
Investigator Assessments						
Reconstitution/Preparation Questionnaire		X				
Investigator Treatment Session Questionnaire 		X				
CCI						

1. Screening and treatment/baseline visits can be performed at the same day
2. Only to be conducted if no screening visit has been performed. Changes to medical history should be asked for if the screening and baseline visits are not performed on the same day.
3. AEs are collected from treatment to the end of the subject's participation, for details how to follow-up ongoing AEs at the last visit see section [7.2.1.1.5](#).
4. Only for women of childbearing potential
5. Subjects in the powder BoNT-A treatment group will be followed 1 month and subjects in the Alluzience treatment group will be followed for 6months.
6. Only for Alluzience-treated subjects
7. Only to be completed once for each Treating Investigator, per study product, after all enrolled subjects have completed Visit 2.
8. Performed pre-treatment

CONFIDENTIAL

Page 17 of 71

*Effective*

GALDERMA EST. 1981	Title 05PF2005 Clinical Study Protocol - STAR	Doc id MA-48441
-----------------------	---	---------------------------

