## 5.5 Procedures/Reasons for Subject Discontinuation

An Investigator may decide to discontinue a subject from the clinical study for medical or safety reasons.

Although the importance of completing the entire clinical study should be explained to the subject by the clinical study personnel, any subject is free to discontinue participation in this clinical study at any time and for whatever reason, specified or unspecified, and without any prejudice. No constraints are to be imposed on the subject, and when appropriate, a subject may be treated with other conventional therapy when clinically indicated.

When a subject does not complete the clinical study, s/he will be fully assessed if such assessment is possible. The procedures designated for the Month 1 (powder BoNT-A treatment group) or the Month 6 (Alluzience treatment group)/Early Termination (ET) visit should be completed for all subjects discontinuing the clinical study and the appropriate eCRF should be completed.

All discontinuations and the reason for discontinuation are to be documented by the Investigator on the eCRF exit form. For discontinuation due to an AE, the AE form is to be completed. The Investigator should also ensure that the subject receives suitable therapy for the AE.

Potential reasons for discontinuation are listed below:

- Adverse Event: Complete an AE form.
- Withdrawal by Subject: Includes consent withdrawal, subject relocation, schedule conflicts, etc. Explain the reason for withdrawal in the comment section of the eCRF exit form.
- Lost to Follow-up: Confirmed by e.g., calling three times at different hours and leaving messages, if applicable, before declaring the subject lost to follow-up. Explain in the comment section of the eCRF exit form.
- Other: This category is to be used for a subject who discontinues due to a reason other than as specified in the predefined categories above. Explain the reason for discontinuation in the comment section of the eCRF exit form.

A subject who has been randomized and assigned a kit number/randomization number cannot be replaced by another subject if he/she discontinues the clinical study for any reason. Additional subjects may be enrolled (randomized/assigned to treatment) in order to attain the number of evaluable subjects. Under no circumstances shall subjects be enrolled more than once.

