6.0 SUBJECT DISPOSITION

Overall subject disposition will include the number of subjects screened, the number of subjects randomized to each treatment arm, the number of subjects in each analysis population (safety, FAS, and PP populations), and the number of subjects who withdrew from the study and the reasons for withdrawal.

Subject disposition by visit will show the number of subjects who completed each visit for the FAS population. Listings of screen failures (including inclusion/exclusion criteria) will be also presented.

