10.2 Secondary Efficacy Analysis

All secondary endpoints will be analyzed by treatment group using n and percentages for each proportion. The proportion of answers to each question will be presented by visit and treatment.

[figure not shown]
CCI

Sponsor: Galderma

[figure not shown]
Protocol Name: STAR

Plan Version: 1.0

CCI

CCI

[figure not shown]

Sponsor: Galderma

Protocol Name: STAR

Plan Version: 1.0

CCI

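### No readable rule keeps early-termination assessments in the Alluzience arm out of the Month 6 summaries, because both share the label Visit 6/ET and the SAP tabulates by recorded visit

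*SAP*

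**What the plan says.** Protocol 5.5 tells the site what to do when a subject leaves early: "The procedures designated for the Month 1 (powder BoNT-A treatment group) or the Month 6 (Alluzience treatment group)/Early Termination (ET) visit should be completed". For Alluzience this applies whenever she leaves. Protocol Table 2 gives the last visit a single column, "Visit 6/ET EoS Group 1", and SAP Appendix A repeats it. SAP 4.1.1 lists six Alluzience visits, and none is a separate ET visit.

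SAP 4.2 is titled Visit Windows but sets no analysis windows. Its tabulation rule is "All data will be tabulated per the evaluation visit as recorded on the eCRF". Its one stated exception is "Questionnaire scores for unscheduled visits will only be included in data listings", and ET is not named there. SAP 7.5.1 treats a visit outside its protocol window as a deviation and summarises how far out it was, up to a category of 21 days or more. It does not move or remove the data. For disposition, SAP 6.0 says "Subject disposition by visit will show the number of subjects who completed each visit for the FAS population".

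**The concern.** Read together, these rules let an assessment made at, say, week 12 be tabulated as a Month 6 result. That matters because Protocol 2.1 makes efficacy of a single Alluzience dose over six months a study aim, and the protocol's own background data show an effect that depends strongly on time since injection. A Month 6 row that contains earlier assessments would not estimate what its label says, and with a waning effect the likely error is towards longer persistence.

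There are two side effects. A subject who left early could be counted as having completed Visit 6. Pooling would also work much like carrying the last observation forward, which sits badly with the observed-case rule in Protocol 9.1.1.4, because a subject with an ET record under Visit 6 would not appear as missing at Month 6.

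**Working it through.** The plan states no dropout rate or Month 6 figure that bears on this, so there is nothing to reproduce. The check has three parts.

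**1. How far an early exit lies from Month 6.** Both schedules set one month at 28 days, with a window of ±7 days. Protocol Table 2 adds that "Visit windows are calculated from Baseline/Visit 2 if not otherwise specified". The Month 6 target is therefore 6 × 28 = 168 days after Baseline, with a window of 161 to 175 days. An exit at Month 5 falls 168 − 140 = 28 days before the target, at Month 3 it is 168 − 84 = 84 days, and at Month 1 it is 168 − 28 = 140 days.

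**2. Whether any readable rule takes such a record out.**

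| Place | Effect on an early ET record |
|---|---|
| SAP 4.2, tabulation rule | Stays under the recorded visit |
| SAP 4.2, unscheduled visits | ET not named |
| SAP 7.5.1 | Flagged as out of window, not moved |
| SAP 6.0 | Counts visits completed, no ET exception |
| SAP 4.0 and much of 10.2 | Redacted, cannot be checked |

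No readable text removes or re-assigns it.

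**3. Illustrative size.** Let d be the share of records in the Month 6 row that come from ET visits. The documents give no value, so d is assumed.

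Apparent Month 6 rate = (1 − d) × rate at Month 6 + d × rate at the time of exit

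The rates come from Protocol Table 3 (investigator assessment: 87.6% at Month 1, 57.6% at Month 3, 17.5% at Month 5, 10.0% at Month 6) and Table 4 (self-assessment: 48.8% at Month 3, 15.1% at Month 6). Both tables report earlier pivotal trials. Early leavers are assumed to respond like the average subject at the time they leave.

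Investigator assessment, exit at Month 3:
- d = 2%: 0.98 × 10.0 + 0.02 × 57.6 = 11.0%
- d = 5%: 0.95 × 10.0 + 0.05 × 57.6 = 12.4%
- d = 10%: 0.90 × 10.0 + 0.10 × 57.6 = 14.8%

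The timing of exit matters. At d = 10%:
- exit at Month 1: 0.90 × 10.0 + 0.10 × 87.6 = 17.8%
- exit at Month 5: 0.90 × 10.0 + 0.10 × 17.5 = 10.8%

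Self-assessment, d = 10%, exit at Month 3: 0.90 × 15.1 + 0.10 × 48.8 = 18.5%, against 15.1%.

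**The case against.** The strongest objection is that the eCRF (version 1.0, cited in SAP 1.0) is not among the documents. A shared schedule column shows shared procedures, not how eCRF visits are named. If the eCRF has its own ET visit, SAP 4.2 as written already produces a separate row. The heading of Protocol 8.1.4 groups the ET visit with Visits 4, 5 and 6 together, so the tie to Visit 6 alone is not uniform. SAP 4.0 (general conventions) and much of 10.2 are redacted and may hold a rule. This stands. A reader might infer that early leavers certainly are reported at Month 6, but the documents support only the conditional statement.

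The size is also uncertain, and that stands too. The affected Month 6 efficacy endpoints cannot be read. The responder rates come from earlier trials and are not a readable endpoint here. ET records may be few: the study gives a single injection, Protocol 5.5 asks for the assessment only where possible, and Protocol 11.4 bars new data after consent is withdrawn.

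Early exits would not be hidden. SAP 6.0 reports withdrawals with reasons, Protocol 9.1.3 lists each withdrawn subject with date and last visit, SAP 7.5.1 summarises out-of-window visits, and the listings show study day. This limits the harm to the completion count, but none of these outputs corrects the Month 6 efficacy row.

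Three wider readings are tempting but not supported:
- **Secondary endpoints.** SAP 10.2 says "The proportion of answers to each question will be presented by visit and treatment", which might suggest that the readable secondary results are exposed. Those questionnaires are all completed at Visit 2.
- **Safety.** The readable adverse event tables are by subject and event, not by visit.
- **Powder arm.** Its Visit 3 column carries no ET label, and the readable content of that visit includes no waning outcome.

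**Conclusion.** The point holds in conditional form. The tabulation rule in SAP 4.2 is readable and stated without an ET exception. Combined with the shared visit label, it would put Alluzience ET assessments made well before Month 6 into the Month 6 by-visit efficacy summaries and the Visit 6 completion count, unless the eCRF labels ET separately or a redacted section deals with it. The likely direction is overstated persistence. The 1.0 to 4.8 point shift (11.0% to 14.8% against 10.0%) is an illustration, not a forecast. It assumes 2% to 10% of Month 6 records come from Month 3 exits, rates like those in Table 3, and leavers who are typical of their time point. It is smaller for later exits or if subjects leave because the effect has worn off.

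The primary endpoint (preparation time) and the readable secondary endpoints are unaffected. The powder arm is followed for one month only, so no between-arm comparison at Month 6 can be distorted.

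**What to change.** First check how eCRF version 1.0 labels an ET visit. Whatever the answer, state the rule in SAP 4.2 so that it does not depend on a page label:

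- Keep tabulation as recorded for scheduled visits.
- Assign an Alluzience ET assessment to the scheduled visit whose protocol window contains its actual date, provided that visit has no record of its own. In days after Baseline, the windows are 21 to 35 (Month 1), 77 to 91 (Month 3), 133 to 147 (Month 5) and 161 to 175 (Month 6). SAP 4.2 adds one to the date difference, so in its relative study days each limit is one higher, for example 162 to 176 for Month 6.
- Otherwise show the assessment in a separate ET row or listing and leave it out of Month 6.
- In the SAP 6.0 table, count an ET visit as a completed Visit 6 only if it falls in the Month 6 window. A scheduled Month 6 visit held outside its window still counts as completed and is flagged under SAP 7.5.1.

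The cost is a few SAP sentences and a derivation from visit dates already collected. No new data or protocol amendment is needed. The downside is slightly fewer observations at Month 6.
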